5.1 General Considerations

Statistical analysis of this study will be the responsibility of Eli Lilly and Company (hereafter, Lilly) or its designee.

Not all displays and analyses described in this SAP will necessarily be included in the clinical study report (CSR). Not all displays will necessarily be created as a "static" display. Some displays may be incorporated as interactive display tools such as Spotfire instead of or in addition to a static display. Any display described in this SAP and not provided in the CSR would be available upon request.

Any change to the data analysis methods described in the protocol will require a protocol amendment ONLY if it changes a principal feature of the protocol. Any other change to the data analysis methods described in the protocol and the justification for making the change will be described in the CSR.

Additional exploratory and or sensitivity analyses of the data may be conducted as deemed appropriate. Some of these additional supplementary analyses may be prespecified in a separate supplemental SAP.

5.1.1 Analysis Methods

Unless otherwise specified, efficacy analyses will be conducted on PAS population, and safety analyses will be conducted on the safety populations as described in Section 4. Summaries will be presented by intervention group in Study AMAX and by the intervention received in the originating study.

Descriptive statistics will include the number of participants; mean, standard deviation, median, minimum, and maximum for continuous measures; and frequency counts and percentages for categorical measures.

For assessments of the co-primary endpoints and other binary efficacy and health outcomes endpoints, the following will be provided unless otherwise specified:

• unadjusted proportions along with the 2-sided 95% confidence intervals using the Wilson Score method (Wilson 1927; Newcombe 1998).

The primary method for binary endpoints will utilize the Wilson Score method. Additional missing data imputation methods for binary endpoints are specified in Section 5.1.5.

For continuous endpoints with more than one post baseline timepoint, the least squares mean from a restricted maximum likelihood based mixed effects model of repeated measures (MMRM) with the corresponding 95% confidence interval may be summarized. The MMRM model will include baseline value, intervention group (Section 5.1.4), visit, and visit by intervention group interaction. Alternative versions of MMRM may be implemented as deemed appropriate. The covariance structure to model the within-participant errors will be unstructured. If the unstructured covariance matrix results in a lack of convergence, the heterogeneous

Toeplitz covariance structure followed by the heterogeneous autoregressive covariance structure will be used. The Newton-Raphson with ridging optimization technique will be used to aid with convergence. The Kenward-Roger method will be used to estimate the denominator degrees of freedom. If the listed methods result in a lack of convergence, analysis may be limited to data through Week 52 of Study AMAX. Following, the model may be updated to remove the visit by intervention received in Study AMAM interaction. If the model fails to converge after the interaction term has been removed, MMRM may not be used for analysis. Unless otherwise specified the MMRM analysis will be performed only for patients originating from AMAM.

For variables that are not collected at each postbaseline visit, data may exist at visits where the variable was not scheduled to be collected. In these situations, data from the early discontinuation visit that do not correspond to the planned collection schedule will be excluded from the MMRM analysis (Andersen and Millen 2013). As the MMRM method accounts for missing data under the missing at random assumption, no other missing data techniques will be used with the MMRM model.

For all change from baseline measures of continuous efficacy, health outcomes, and quality of life endpoints, the least squares mean and the corresponding 95% confidence interval from analysis of covariance (ANCOVA) will be summarized. The ANCOVA model will include baseline value, and intervention group (see Section 5.1.4) in the model. Additional continuous endpoints that are not change from baseline will be presented as summaries. Unless otherwise specified the ANCOVA analysis will be performed only for patients originating from CCI.

Missing data imputation method for the ANCOVA model and summaries are specified in Section 5.1.5.

All analyses of safety data will be presented as summaries.

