9.4.1.4. Missing Data Imputation

While every effort will be made to reduce missing data, the missing data imputation methods described below will be used to assess the efficacy endpoints when participants are permanently discontinued from study drug or otherwise have missing data.

- Nonresponder imputation (NRI): For analysis of categorical efficacy and health outcomes variables, missing data will be imputed using an NRI method. Participants will be considered a Nonresponder for the NRI analysis if they
 - do not achieve the endpoint(s) being analyzed
 - have missing data at the time point of interest that results in nonassessment of (an) endpoint(s) at the time point of interest, or
 - discontinue treatment prior to the time point of interest due to reasons other than participants switching to commercially available mirikizumab or extraordinary circumstances, e.g., inability to supply study drug to a particular region
- Mixed-model for repeated measures: For continuous variables, the analysis may include the MMRM with the missing-at-random assumption for handling missing data. This analysis takes into account both missingness of data and the correlation of the repeated measurements. Additional details will be provided in the SAP.
- Modified Baseline Observation Carried Forward with ANCOVA: For continuous variables, single imputation will be used based on carrying the baseline observation forward. Additional details will be provided in the SAP.

Additional details and sensitivity analyses, including imputed and observed data, will be specified in the SAP.

Methodology to address missing data due to participants switching to commercially available mirikizumab or extraordinary circumstances, e.g., inability to supply study drug to a particular region, will be addressed in the SAP.

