- For the additional ICE where participants discontinue due to commercial availability and extraordinary circumstances including study treatment supply issues and the site termination, a hypothetical scenario is envisaged in which these patients remained for the rest of the study, leading to a missing data problem. Participants with the ICE will be excluded from analysis for timepoints of interest after the ICE. The assumption behind this approach is that measurements after this ICE are missing completely at random and thus the estimation can be implemented using observed values.

For all participants with sporadically missing observations prior to any ICEs, the last non-missing observation before the sporadically missing data will be carried forward.

Mixed-effects Model for Repeated Measures (MMRM)

As a sensitivity analysis for continuous variables with multiple postbaseline measurements in a study period, the MMRM approach will be used with the missing at random assumption for handling missing data. This analysis takes into account both missingness of data and the correlation of the repeated measurements.

For continuous endpoints, a hybrid estimand strategy is used:

- For ICEs of study intervention discontinuation due to reasons other than commercial availability and extraordinary circumstances including study treatment supply issues and the site termination, the composite strategy will be used such that measurements after the ICEs will return to baseline. As such, these patients are not considered missing from the perspective of the estimand of interest.
- For the additional ICE where participants discontinue due to commercial availability and extraordinary circumstances including study treatment supply issues and the site termination, a hypothetical scenario is envisaged in which these patients remained for the rest of the study, leading to a missing data problem. Assuming measurements after this ICE can be considered as missing at random, the MMRM approach can be used to handle the missing data.

The MMRM approach will also be used to handle sporadic missingness.

Modified Nonresponder Imputation (mNRI)

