5.4.1.3 Sensitivity Analysis

Refer to Section 5.3.3 for details regarding the methods used for sensitivity analyses that may be used for binary secondary endpoints. Additional details are described in Appendix 2 Section 6.2.

For continuous endpoints, MMRM will be used as sensitivity analysis (see Section 5.1.5).

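### SAP 5.1.1 rules out any further missing-data technique with the MMRM, while SAP 5.1.5 and the SAP 1.1 estimand require return to baseline after ordinary discontinuation in that same model

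*SAP*

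**What the plan says.** By an ordinary stop I mean discontinuation of study drug for any reason apart from commercial availability or extraordinary circumstances such as supply failure or site closure. Stopping for lack of benefit or for an adverse event falls in this class.

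- **SAP 5.1.1** describes the MMRM as handling missing data under MAR and states that "no other missing data techniques will be used with the MMRM model". The section sends the reader onward only for other analyses: "Missing data imputation method for the ANCOVA model and summaries are specified in Section 5.1.5". The MMRM is not named there.
- **SAP 5.1.5**, in the paragraph headed for the MMRM, says that after an ordinary stop "the composite strategy will be used such that measurements after the ICEs will return to baseline", and that "these patients are not considered missing from the perspective of the estimand of interest". MAR is kept for two cases only. One is sporadic gaps. The other is stops due to availability or extraordinary circumstances: "Assuming measurements after this ICE can be considered as missing at random, the MMRM approach can be used to handle the missing data".
- **SAP 1.1** sets the same return-to-baseline rule as the estimand strategy for continuous endpoints.
- **SAP 5.4.1.3** gives the model its role: "For continuous endpoints, MMRM will be used as sensitivity analysis", with a reference to 5.1.5. The main analysis is ANCOVA with mBOCF (SAP 5.1.5 and 5.4.1.2).
- **Protocol 9.4.1.4** leaves the MMRM details to the SAP. For the mBOCF ANCOVA it says that "single imputation will be used based on carrying the baseline observation forward".

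**The concern.** The two SAP sections give different instructions for the same visits of the same participants. Someone who stops drug has an early termination visit and then Visits 801 and 802 (Protocol 7.1). The visible rows of Table AMAX.1-3 show no clinician CDAI and no diary at 801 or 802, and Protocol 8.1.1.2 allows no early-termination endoscopy in follow-up. For these measures, later scheduled visits are therefore empty after an ordinary stop. A programmer working from 5.1.1 leaves them empty and lets the model predict them. A programmer working from 5.1.5 enters the originating-study baseline value.

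What is at stake is the meaning of the sensitivity analysis. A sensitivity analysis should vary the assumptions behind one estimand. Under 5.1.1 the MMRM changes the estimand for ordinary stoppers, from failure (return to baseline) to a hypothetical in which they stayed on treatment. A difference from the ANCOVA could then not be read as sensitivity to assumptions. In an open-label study, the choice between the two rules should not be left until data are in hand.

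**Working it through.** **Step 1. Compare the rules for each type of missing value.**

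| Situation | SAP 5.1.1, read literally | SAP 5.1.5, MMRM paragraph | Agree? |
|---|---|---|---|
| Sporadic gap on treatment | MAR | MAR | Yes |
| Stop for availability or extraordinary circumstances | MAR | MAR, hypothetical strategy | Yes |
| Ordinary stop | MAR | Value set to baseline, composite strategy | No |

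The conflict is confined to the last row, where SAP 1.1 sides with 5.1.5.

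**Step 2. Write down the difference.** The plan states no figure to reproduce. Let *d* be the share with an ordinary stop before the visit, *S* the mean change in those continuing, and *P* the mean change that MAR predicts for the stoppers. Other missing data are ignored.

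- MAR mean = (1 − d)·S + d·P
- Return-to-baseline mean = (1 − d)·S + d·0
- Difference = d·P

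On a score where a fall is improvement, MAR looks better when P is negative. If P is positive, meaning that stoppers are predicted to be worse than originating-study baseline (the efficacy baseline in SAP 5.1.2), return to baseline looks better. The direction is therefore usual but not guaranteed.

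**Step 3. Illustrate the size.** The rates below are assumptions, because the documents give none. Two cases were taken.

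- *Closed form:* stoppers would have followed the group mean D, so P = D, the gap is d·D and the return-to-baseline mean is (1 − d)·D.
- *Simulation:* 40,000 participants, three visits, D = −1 SD, correlation 0.6, with stopping more likely after a poor last value. The MAR maximum-likelihood mean at the last visit is compared with the return-to-baseline mean.

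| d | Closed form: return to baseline | Gap | Simulation: MAR | Simulation: return to baseline | Gap |
|---|---|---|---|---|---|
| 5% | 0.95·D | 5% | −0.998 | −0.975 | 0.023 (2%) |
| 10% | 0.90·D | 10% | −1.002 | −0.953 | 0.049 (5%) |
| 20% | 0.80·D | 20% | −0.993 | −0.884 | 0.109 (11%) |
| 30% | 0.70·D | 30% | −0.999 | −0.821 | 0.178 (18%) |

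The realised rate in the last simulated row was 29.5%. Across both cases the gap runs from about 2% to 30% of the mean change. The simulated gaps are smaller because those who stopped had been doing worse. At 30%, the implied P is 0.178 / 0.295 = 0.60 of D.

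**Step 4. Trace what is touched.** The co-primary endpoints are binary and use nonresponder imputation with Wilson intervals (SAP 5.3.2). The main continuous analysis is the mBOCF ANCOVA. Neither uses the 5.1.1 sentence.

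**The case against.** The strongest reply is that the sections can be read in sequence. SAP 5.1.5 says of ordinary stoppers that "these patients are not considered missing from the perspective of the estimand of interest". Setting them to baseline is then handling of an intercurrent event, and the 5.1.1 sentence governs only what is still missing afterwards. SAP 5.4.1.3, which calls for the analysis, cites 5.1.5 and not 5.1.1. The SAP version history says that 5.1.5 was revised to match the updated estimands. So the intended rule is recoverable, and a reader who infers that the sections are beyond reconciliation goes too far.

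This shows which rule is meant, but it does not remove the contrary one. SAP 5.1.1 does not mention the sequence, and its pointer to 5.1.5 covers ANCOVA and summaries only. The return-to-baseline rule itself sits in a section on missing-data imputation, and Protocol 9.4.1.4 calls carrying baseline forward single imputation. Appendix 2 does not settle the matter, because no visible row lists the MMRM.

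The protocol's amendment log records that a similar sentence was taken out of the protocol to fit the planned estimand. That is superseded text. It hints that the SAP sentence was left over, and it is not itself an error.

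Two further limits stand. A reader might infer that the MMRM is the only check on the continuous results. It is not: SAP Section 4 assigns the mITT population to sensitivity analyses, and Appendix 2 lists as-observed results. The MMRM is also optional in 5.1.1 and may be dropped if it does not converge, although 5.4.1.3 is firmer.

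**Conclusion.** The inconsistency is real and lies between sections of the current SAP. Taken literally, 5.1.1 gives an MMRM aimed at a stay-on-drug estimand, which differs from the estimand in SAP 1.1 and from the mBOCF ANCOVA that the MMRM is meant to support. The sentence should be corrected before the analysis is run.

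The size is roughly 2% to 30% of the mean change at assumed ordinary-stop rates of 5% to 30%. It depends on how stoppers compare with stayers and rests on no rate in the documents. Two stronger readings are tempting and are not supported:

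- *The gap equals the discontinuation rate.* On an assumed CDAI change of −150, this would be 15, 30 and 45 points at 10%, 20% and 30%. It holds only if stoppers would have done as well as everyone else, which is doubtful for people who stop for lack of benefit.
- *The MMRM is bound to flatter the drug.* It usually would under 5.1.1, but the sign turns if modelled values fall below originating-study baseline.

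The consequence is limited. No hypothesis is tested (Protocol 9.1), and the co-primary results and the main ANCOVA do not change.

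**What to change.** In SAP 5.1.1, replace the sentence with wording such as: *After the Section 5.1.5 rule has been applied (values following a stop not caused by commercial availability or extraordinary circumstances set to baseline), remaining missing values are handled by the MMRM under MAR, with no further imputation.* Extend the 5.1.1 pointer to 5.1.5 so that it names the MMRM as well.

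If a pure-MAR MMRM is also wanted, list it separately as supplementary and state its hypothetical estimand.

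The cost is a sentence or two in the SAP and one data-preparation step before the model is fitted. Compared with a literal reading of 5.1.1, the reported MMRM means would usually be somewhat less favourable.

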5.1.2 Definition of Baseline

Unless otherwise specified, all references to baseline for efficacy and health-outcome-related endpoints in this study refer to baseline values of the originating study (that is, the study in which the participant received their first dose for the mirikizumab Crohn's Disease development program). Unless otherwise specified, all references to baseline for safety analyses refer to baseline values of Study AMAX.

Change from baseline will be calculated as the visit value of interest minus the baseline value. If a baseline value or the value at the visit is missing for a particular variable, then the change from baseline is defined as missing.

5.1.3 Definition of Study Period Time Interval

The table below displays a list of study periods along with the definition of which participants will be considered to have entered the study period and when the individuals start and end the study period. The table shows both a date and a time.

To calculate the length of any time interval or time period in this study the following formula will be used:

 $Length\ of\ interval\ (days) = End\ Date - Interval\ Start\ Date + 1$

To convert any time length from days to years, the following formula will be used:

Length of interval (years) = Length of interval (days)/365.25

To convert any time length from days to weeks, the following formula will be used:

Length of interval (weeks) = Length of interval (days)/7

Only for the purpose of calculating the length of study period time intervals, the words "prior to" in the table below should be understood to mean "the day before" while the words "after" should be understood to mean "the day after." For the purpose of determining whether a date/time lies within an interval these words are intended to convey whether the start or end of the period is inclusive of the specified date.

Study Period	Interval Start Definition	Interval End Definition
Induction Period	At the date/time ^a of first dose of study intervention in Study AMAX. For participants who are assigned but not dosed, Induction Period starts on the date of study intervention assignment.	Prior to the start of Long-Term Extension Period. For participants who discontinue before or CCI visit, Induction Period ends at the latest date of study intervention discontinued date or last study intervention visit date.
Long-Term Extension Period	At the Week 12 dosing date/time ^a in Study AMAX. If the participant is unable to be dosed at the Week 12 visit, the Long-Term Extension Period starts at the Week 12 Visit. If the participant misses the Week 12 visit, the Long-Term Extension Period starts at Day 92.	After the CCI visit date. For participants who discontinue prior to CCI , Long-Term Extension Period ends at the latest date of study intervention disposition date or last study intervention visit date.
Follow-up Period	All participants who had Visit 801 or Visit 802 are considered to have entered the Follow-up Period. The latest of Induction Period or Long- Term Extension Period interval end date.	The last date of the last study visit and study disposition date.
Complete Study Period	At the date/time ^a of first dose of study intervention. For participants who are assigned but not dosed, Complete Study Period starts on the date of study intervention assignment.	After the CCI visit date. For participants who discontinue prior to CCI, Complete Study Period ends at the latest date of study intervention disposition date or last study intervention visit date.

	At the date/time ^a of first dose of study intervention. For	
Complete Study Period +	participants who are assigned	The last date of the last study visit within
Continued Access Period	,	Continued Access Period.
	Period starts on the date of	
	study intervention assignment.	

Missing dose time will be imputed as the earliest time that is consistent with available data about dose time. For example, suppose the minutes are missing but hour is present. In this case, we would impute the minutes to be 0.

5.1.4 Definition of Study Intervention by Study Period

The table below provides the study intervention groups to be displayed for each analysis population and analysis period.

Analysis	Analysis Period	Study Intervention Groups:
Population		
PAS/mITT/Safety population	Induction Period/Complete Study Period/ Continued Access Period	 AMAM miri/miri/ SC AMAM pBO/miri/ SC AMAM PBO/miri/ IV AMAM PBO/miri/ IV AMAM uste/uste/ SC AMAM uste/uste/ IV AMAM PBO/PBO/ SC AMAM PBO/PBO/ IV AII AMAM/ SC a All AMAM/ IV a All AMAM a All AMAM/ SC a Total a
PAS/mITT subset populations	Complete Study Period	PAS/mITT sub-population – Endoscopic Responder in the originating study: • AMAM miri/miri/ SC (co-primary analysis) • AMAM PBO/miri/ SC • AMAM uste/uste / SC • AMAM PBO/PBO/ SC • All AMAM SC a • Total a PAS/mITT sub-population – Endoscopic Nonresponder in the originating study: • AMAM miri/miri / IV • AMAM PBO/miri/ IV • AMAM uste/uste / IV • AMAM PBO/PBO/ IV • AMAM PBO/PBO/ IV • All AMAM IV a • Total a

Analysis Population	Analysis Period	Study Intervention Groups:		
		Other sub-population analysis:		
		 AMAM miri/miri/ SC AMAM miri/miri/ IV AMAM PBO/miri/ SC AMAM PBO/miri/ IV AMAM uste/uste/ SC AMAM uste/uste/ IV AMAM PBO/PBO/ SC AMAM PBO/PBO/ IV AII AMAM/ SC a All AMAM/ IV a All AMAM a All AMAM a Total a 		

Abbreviations: AMAG = Study I6T-MC-AMAG; AMAM = Study I6T-MC-AMAM; IV = intravenous; miri = mirikizumab; PBO = placebo; SC = subcutaneous; uste = ustekinumab; Q4W = every 4 weeks.

For endpoints utilizing the PAS/mITT subset populations, not all intervention groupings listed above may be shown.

5.1.5 Missing Data Imputation

Intercurrent events (FDA 2017) are events which occur after the study intervention initiation and make it impossible to measure a variable or influence how it should be interpreted. Section 1.1 includes intercurrent events for the primary and secondary endpoints. The missing data methods described below may be used to address the intercurrent event strategies proposed for this study.

Non-Responder Imputation

A hybrid estimand strategy will be used to handle binary endpoints:

- Patients who discontinue study treatment due to reasons other than commercial availability and extraordinary circumstances including study treatment supply issues and the site termination, are categorized as treatment failures after discontinuation. As such, these patients are not considered missing from the perspective of the estimand of interest.
- The hypothetical strategy will be used to handle the ICE of study treatment discontinuation due to commercial availability and extraordinary circumstances including study treatment supply issues and the site termination. Participants with the ICE will be excluded from analysis for timepoints of interest after the ICE. The assumption behind this approach is that measurements after this ICE are missing completely at random and thus the estimation can be implemented using observed values.

^a Unless otherwise specified, these treatment arms are not included in the modeling to estimate treatment effect for MMRM and ANCOVA analysis. Also these treatment arms may be excluded from some tables or figures to simplify the output.

A small number of patients who completed study treatment up to the time point of interest but are sporadically missing the binary endpoint data will still require imputation. These patients will be imputed using NRI.

Modified Baseline Observation Carried Forward (mBOCF)

As a primary analysis for continuous variables, the ANCOVA with mBOCF approach will be used for handling missing data. For continuous endpoints a hybrid estimand strategy is used:

- For ICEs of study intervention discontinuation due to reasons other than commercial
 availability and extraordinary circumstances including study treatment supply issues and
 the site termination, the composite strategy will be used such that measurements after the
 ICEs will return to baseline. As such, these patients are not considered missing from the
 perspective of the estimand of interest.
- For the additional ICE where participants discontinue due to commercial availability and extraordinary circumstances including study treatment supply issues and the site termination, a hypothetical scenario is envisaged in which these patients remained for the rest of the study, leading to a missing data problem. Participants with the ICE will be excluded from analysis for timepoints of interest after the ICE. The assumption behind this approach is that measurements after this ICE are missing completely at random and thus the estimation can be implemented using observed values.

For all participants with sporadically missing observations prior to any ICEs, the last non-missing observation before the sporadically missing data will be carried forward.

Mixed-effects Model for Repeated Measures (MMRM)

As a sensitivity analysis for continuous variables with multiple postbaseline measurements in a study period, the MMRM approach will be used with the missing at random assumption for handling missing data. This analysis takes into account both missingness of data and the correlation of the repeated measurements.

For continuous endpoints, a hybrid estimand strategy is used:

- For ICEs of study intervention discontinuation due to reasons other than commercial availability and extraordinary circumstances including study treatment supply issues and the site termination, the composite strategy will be used such that measurements after the ICEs will return to baseline. As such, these patients are not considered missing from the perspective of the estimand of interest.
- For the additional ICE where participants discontinue due to commercial availability and extraordinary circumstances including study treatment supply issues and the site termination, a hypothetical scenario is envisaged in which these patients remained for the rest of the study, leading to a missing data problem. Assuming measurements after this ICE can be considered as missing at random, the MMRM approach can be used to handle the missing data.

The MMRM approach will also be used to handle sporadic missingness.

Modified Nonresponder Imputation (mNRI)

For the co-primary endpoints and selected secondary endpoints, missing data will be imputed using hybrid multiple imputation as a sensitivity analysis. Missing data for reasons of treatment discontinuation due to commercial availability and extraordinary circumstances including study treatment supply issues and the site termination will be imputed by multiple imputation (MI), while missing data due to treatment discontinuation for reasons other than commercial availability and extraordinary circumstances including study treatment supply issues and the site termination will be categorized as non-responders. Sporadically missing data (i.e., when a patient was still in the treatment period but data was not collected) will be imputed by MI.

As Observed Analysis

For some endpoints, patients who are missing the endpoint data for a specific visit for any reason including intercurrent events will be excluded from the analysis for that visit. Simple descriptive summaries will be presented.

[figure not shown]
